#### Run in Phase (4 weeks)

At this initial visit, whether in person or via telephone, participants will be screened for inclusion/exclusion and data on their demographics, headache characteristics, current and past treatments, and medical history will be collected. Those meeting criteria for further participation will be trained on how to use the headache diary. Patients will be instructed to keep a prospective headache diary for the next 4 weeks. We assume that up to 25% of individuals participating in the run-in phase will not meet the migraine day frequency inclusion criteria and/or diary compliance minimum and thus will not continue in this study.

#### Baseline (first treatment) Visit

Patients will return for a baseline visit after 4 weeks (i.e. 28 days +/- 3 days since start of run-in phase) of prospective headache diary collection. Diary compliance and eligibility for study inclusion will be assessed. Patients who still meet eligibility criteria will have measurement of vital signs and urine pregnancy testing will be conducted for women of childbearing potential. Levels of depression and anxiety will be measured using the Beck Depression Inventory and State-Trait Anxiety Inventory, respectively. Functional disability will be assessed with the Migraine Disability Assessment (MIDAS) and the Migraine Functional Impairment Questionnaire (MFIQ). Symptoms of cutaneous allodynia will be assessed using the Allodynia Symptom Checklist 12. Symptoms of cognitive dysfunction associated with migraine will be assessed using the Mig-Scog Questionnaire. (24, 25) Patients will undergo

quantitative sensory testing (QST) for determination of heat pain thresholds and the temperature that results in moderate intensity heat pain. (13, 26, 27) To assess cognitive function, patients will complete two attention tasks; a computer version of the n-back task and Trails A and B.

### Case Report Forms

Case report forms include:

- 1) Inclusion and Exclusion Criteria
- 2) Contact Information
- 3) Demographics: birthdate, gender, race, ethnicity, handedness
- 4) Vital Signs
- 5) Urine Pregnancy Test Results (for women of childbearing potential)
- 6) Headache Characteristics: headache frequency, duration, location, quality, intensity; associated symptoms; aura; number of years with migraine; current preventive and acute therapies
- 7) Personal Medical History
- 8) Current Medications and Non-Medication Treatments
- 9) Prior Migraine Medications
- 10) Migraine Functional Impact Questionnaire (MFIQ)
- 11) Beck Depression Inventory (BDI)
- 12) State-Trait Anxiety Inventory (STAI)
- 13) Migraine Disability Assessment (MIDAS)
- 14) Allodynia Symptom Checklist 12 (ASC-12): ictal and interictal
- 15) Migraine Scog
- 16) N-back task
- 17) Trails A and B
- 18) Quantitative Sensory Testing Results
- 19) Two Week Follow-up Headache Characteristics
- 20) Four Week Follow-up Headache Characteristics
- 21) Eight Week Follow-up Headache Characteristics
- 22) Twelve Week Follow-up Headache Characteristics
- 23) Patient Global Impression of Change
- 24) Adverse Events
- 25) Headache Diary
- 26) 26 Connor-Davidson Resilience Scale 25 (CD-RISC-25)

The case report forms are included within Appendix 1.

Questionnaires	First Visit (start of run-in phase)	First Tx Visit	Two-Week Visit	Four-Week Visit (second tx)	Eight-Week Visit	Twelve-Week Visit
Contact Information	X					
Inclusion/Exclusion Criteria	X	X				
Demographics	X					
Headache Characteristics	X	X				
Follow-up Headache Characteristics			X	X	X	X
Current Medications and Other Treatments	X	X	X	X	X	X
Prior Migraine Treatments	X					
Medical History	X					
ASC-12 (ictal/interictal)		X	X	X	X	X
MFIQ		X	X	X	X	X
MIDAS		X				X
BDI		X	X	X	X	X
STAI		X	X	X	X	X
Mig-Scog		X	X	X	X	X
PGIC			X	X	X	X
CD-RISC-25		X	X	X	X	X

Adverse Events	X	X	X	X	X
----------------	---	---	---	---	---

Tx = treatment; ASC-12 = allodynia symptom checklist – 12; MFIQ = migraine functional impact questionnaire; MIDAS = migraine disability assessment; BDI = Beck Depression Inventory; STAI = state-trait anxiety inventory; PGIC = patient global impression of change

### Pain Threshold Testing

QST for determining cutaneous heat pain thresholds has been used extensively in our lab. (13, 26, 27) A Medoc Pathway platform with a 30 mm x 30 mm thermode is used for testing. Heat pain thresholds are determined for the right and the left forearm and for the right and left forehead. The thermode is applied to the skin and fastened with a Velcro strap. The method-of-limits is used: thermode starts at 32 degrees Celsius and increases in temperature at a rate of 1 degree Celsius per second until the subject presses a button on the response unit, indicating that the sensation changed from heat to pain. Testing will be performed three times at each body site and the average of the three measurements will be considered that individuals heat pain threshold.

The temperature required to cause moderately intense heat pain will be determined by using the ramp and hold method. Moderately intense heat pain is defined by an individual rating their pain intensity between 4 and 7 using an 11 point scale in which zero indicates no pain and 10 indicates the most severe pain. Initially, subjects are stimulated for 7.5 seconds with a temperature equal to their heat pain threshold plus 1 degree Celsius. Individuals then rate the pain intensity. If pain intensity is rated below 4, the temperature is increased in 0.5 degree Celsius increments until rated between 4 and 7. Conversely, if the pain intensity is rated greater than 7, the stimulation temperature is decreased in 0.5 degree Celsius increments.

### Imaging Protocol

Brain MRI will be performed on a Siemens 3T scanner at the Mayo Clinic. The MRI paradigm will include: 1) high-resolution T1-weighted imaging allowing for advanced structural analyses such as determining regional volumes, cortical thickness and surface area; 2) T2-weighted imaging to rule out pre-existing structural brain abnormalities (e.g. incidental findings); 3) Diffusion Tensor Imaging (DTI) used for assessing white matter integrity; 4) ten minutes of resting-state Blood Oxygen Level Dependent (BOLD) signal collection for resting state functional connectivity analyses; 5) event-related paradigm during which patients are exposed to cutaneous thermal stimuli causing moderately intense heat pain so that brain responses to pain can be measured; and 6) Arterial Spin Labeling (ASL) to assess cerebral blood flow.

### N-Back Task

For purposes of test standardization and data interpretation, all subjects will complete the computer-based version of the n-back task on one of two MacBook laptops. The software for the n-back task will be downloaded on the laptops and subject task performance will be automatically calculated and summarized- thus eliminating testing bias.

### Trails A and B

Subjects will complete the standardized worksheets of Trails A and B. On Trails A, subjects are asked to connect consecutive numbers from 1-25. On Trails B, subjects are asked to alternate between

connecting numbers and letters. (i.e., 1-A-2-B-3-C, and so forth) Both tests are measuring attention and processing speed. For both tests, number of errors are recorded as well as the number of seconds required to complete each task.

#### Treatment with Erenumab

Patients receive treatment with 140 mg of erenumab via subcutaneous injection during their baseline visit and then again 4 weeks later. Patients will either be taught how to self-inject by a qualified research team member and then will do so under research team observation or receive the injections administered by a qualified research team member. Injections will be administered in the abdomen (except for a two inch area right around the navel), thigh, or outer area of upper arm (if someone else is injecting the patient) according to patient preference and will consist of two consecutive 70 mg injections. The second injection will not be given in the same spot as the first injection.

Erenumab will be stored refrigerated at 2°C to 8°C (36°F to 46°F) until time of use. Once removed from the refrigerator, it will be kept at room temperature and used within 7 days. Prior to administration, erenumab will sit at room temperature for at least 30 minutes, protected from direct sunlight.

#### Daily Headache Diary

A daily headache diary will be completed for the next 12 weeks to allow for assessment of changes in headache and migraine frequency. Headache diary data will be analyzed to classify patients as “responders” (50% or greater reduction in migraine day frequency between weeks 5-8 post first erenumab treatment compared to frequency during the run-in phase) or “non-responders” (less than 50% reduction in migraine day frequency during weeks 5-8 post first erenumab treatment compared to the frequency during the run-in phase). Since patient outcome will be measured at 8 weeks (opposed to 12 weeks like is done in the majority of clinical trials), depending upon patient outcomes other definitions of “response” and “non-response” could be used. Furthermore, correlations between changes in migraine frequency and imaging outcomes could also be assessed.

A migraine day will be defined as follows: any calendar day during which a person experiences a qualified migraine headache (onset, continuation, or recurrence of the migraine headache). A qualified migraine headache is defined as a migraine with or without aura, lasting for at least 30 minutes, and meeting at least one of the following criteria (a and/or b):

- a) At least 2 of the following pain features: unilateral, throbbing, moderate to severe, exacerbated with exercise/physical activity
- b) At least 1 of the following associated symptoms: nausea and/or vomiting, photophobia and phonophobia

If the participant takes a migraine-specific medication (i.e. triptan or ergotamine) during aura or to treat headache on a calendar day, then it will be counted as a migraine day regardless of the duration and pain features/associated symptoms.

Missing values may exist in headache dairy data due to various reasons such as subjects’ missed recording, early withdrawal, or inadequate entries prohibiting evaluation of the end point (responder vs. non-responder). To impute the missing data and allow for evaluation of migraine frequency,

classic imputation methods commonly used in clinical trials will be adopted.(6) Specifically, for months with 20-27 days of dairy data, the values for missing entries will be imputed by prorating scores of 28-day post-treatment periods. That is, monthly migraine frequency can be calculated as the ratio of number of observed migraine days to number of observed days multiplied by 28. For months with less than 10 days of dairy data, monthly migraine frequency will be estimated by the substitution of the patient's previous 28-day period score, multiplied by the ratio of the mean for all patients in the same period to the mean for all patients in the previous period. For post-treatment periods with 10-19 days of diary data, scores will be estimated using a mean of both methods.

**Follow up visits One through Four (see table 1):** Four follow-up visits will be scheduled: at weeks 2, 4, 8 and 12 post-initial treatment with erenumab (week 2 = 14 days +/- 2 days since first visit; week 4 = 28 days +3 days since first visit; week 8 = 56 days +/- 3 days since first visit; week 12 = 84 days +/- 5 days since first visit). The early follow-up at 2 weeks will be utilized for repeat QST, brain imaging and cognitive testing so that data are available for investigating early markers/predictors of treatment response. A second treatment with erenumab will occur during the 4-week visit. Imaging, QST and neurocognitive testing will be repeated during the 8-week visit, allowing for determination of biomarkers for treatment response that might not have been found at the early time-point of 2 weeks and that can be correlated with clinical measures of treatment response (i.e. changes in migraine day frequency). The 12-week visit will allow for further assessment of safety and efficacy.

**Acute Migraine Therapy:** Patients will be allowed to use acute headache treatments including migraine-specific medication (e.g. triptans, ergotamine derivatives) and NSAIDs during the study.

**Other Migraine Preventive Therapy:** Patients will be allowed to use two or fewer migraine preventive therapies in addition to erenumab as long as the dose has been stable for at least 2 months before the start of the run-in phase. Changes to the dose of such treatments will not be allowed during this study unless necessary due to safety issues or lack of tolerability.

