## **Published Work and Preliminary Data**

Our team has performed multiple studies that are directly relevant to the goals of this project and serve as evidence of our ability to successfully conduct this study. We have completed studies comparing noxious heat-induced brain activation patterns in people with migraine vs. healthy controls. (13) These studies showed that migraineurs have greater pain-induced activation in several brain regions, many of which participate in cognitive aspects of pain processing. For several of these regions, the extent of greater activation correlated with the frequency of headaches, serving as strong evidence for a direct relationship between having migraine and greater activation of these pain-processing brain regions and at least suggesting that reductions in headache frequency would correlate with reductions in pain-induced activation. Our resting-state functional connectivity studies have investigated functional connectivity of affective-emotional pain processing regions and of descending pain modulatory brainstem regions. (14, 15) These studies demonstrated that migraineurs have atypical functional connectivity and the extent of atypical connectivity correlates with measures of migraine disease burden such as number of years with migraine and allodynia symptoms. Our structural MRI studies have shown migraineurs to have atypical structure of the brainstem and abnormal cortical thinning with age, aberrant correlations between brain cortical thickness and cutaneous pain thresholds, atypical cortical thickness correlations, and abnormal white matter tract integrity. (16-18) Furthermore, our work has shown migraineurs with interictal photosensitivity to have thicker cerebral cortex in parieto-occipital and fronto-parietal regions. (19) Finally, our machine-learning multivariate pattern analyses have yielded migraine classifiers that use brain structural data to differentiate the brain of an individual chronic migraineur from that of a healthy control (see Figure 1) or episodic migraineur (see Figure 2) with high accuracy (American Headache Society Wolff Award winning paper). (20) Our classifiers based on resting state functional connectivity data differentiate the brain of an individual migraineur from a healthy control with high accuracy (American Academy of Neurology Harold Wolff – John Graham Award winning research, see Figure 3). (20, 21) In addition, we developed a decision support system using multi-modality imaging data to interrogate the utility of combining structural and functional imaging data for migraine patient discrimination and the accuracy of such discrimination. (see Figure 4) (22) Results showed better classification accuracy when combining structural and functional data than using either data type alone.

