**Table 1- Study Flow.**

	Run in Phase (time: -4 wks)	Baseline (time: 0)	First Follow-up (time: 2 wks)	Second Follow-up (time: 4 wks)	Third Follow-up (time: 8 wks)	Fourth Follow-up (time: 12 wks)
Determine Eligibility	X	X				
Questionnaires	X	X	X	X	X	X
QST		X	X		X	
MR Imaging		X	X		X	
Cognitive Testing		X	X		X	
Vital Signs		X	X	X	X	X
Urine Pregnancy Test		X		X		
Erenumab Treatment		X		X		
Headache Diary	X	X	X	X	X	X

**Participants:** Up to 67 adult patients who are at least 18 years of age but younger than 66 years of age with high frequency episodic migraine or chronic migraine with and/or without aura will be enrolled into the run-in phase of this study at Mayo Clinic Arizona. Enrollment will stop once 50 subjects provide headache diary during the run-in phase that meets eligibility criteria (i.e. documented 6-25 migraine days per 28 days). Previously collected data of healthy control subjects (n=50) will be used for data comparison. Exclusion and inclusion criteria will be modeled after those used in the phase 2 and 3 trials of erenumab for the prevention of migraine. (6, 8) In addition, patients who have contraindications to MRI (e.g. metal implants, aneurysm clips, severe claustrophobia) will be excluded from study participation. Potential participants will be excluded if they have active chronic pain conditions other than migraine (e.g. chronic pelvic pain) or acute pain conditions (e.g. recent surgery). Potential participants who have sensory disorders that might affect the perception of cutaneous thermal stimuli will also be excluded (e.g. peripheral neuropathy).

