## **Subject Eligibility**

### *Inclusion Criteria*

- Adults 18-65 years of age

- Episodic migraine (with or without aura) or chronic migraine according to the diagnostic criteria included within the International Classification of Headache Disorders 3 (ICHD-3) (23)
  - Episodic Migraine
    - A. At least 5 attacks fulfilling criteria B-D
    - B. Headache attacks lasting 4-72 hours (when untreated or unsuccessfully treated)
    - C. Headache has at least two of the following four characteristics:
      - a. Unilateral location
      - b. Pulsating quality
      - c. Moderate or severe pain intensity
      - d. Aggravation or causing avoidance of routine physical activity
    - D. During headache at least one of the following:
      - a. Nausea and/or vomiting
      - b. Photophobia and phonophobia
    - E. Not better accounted for by another ICHD-3 diagnosis
  - Chronic Migraine
    - A. Headache (migraine-like or tension-type like) on at least 15 days per month for longer than 3 months, and fulfilling criteria B and C
    - B. Occurring in a patient who has had at least five attacks fulfilling criteria B-D for "episodic migraine" (above)
    - C. On at least 8 days per month for longer than 3 months, fulfilling any of the following:
      - a. Criteria C and D for migraine without aura
      - b. Criteria B and C for migraine with aura
      - c. Believed by the patient to be a migraine at onset and relieved by a triptan or ergot derivative
    - D. Not better accounted for by another ICHD-3 diagnosis
- 6-25 migraine days per month on average over the 3 months prior to screening, confirmed by run-in phase prospective data collection
- Duration since migraine onset of at least 12 months prior to screening based on medical records and/or patient self-report

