#### Analysis Plans

*Specific Aim #1 (i.e. identify changes in brain structure and function that correlate with response to erenumab):* Pre-treatment and post-treatment MRI data will be used for within and between subject

comparisons. Within subject analyses will compare baseline brain activation and perfusion patterns and functional connectivity patterns pre-treatment to post-treatment. Between subject group analyses will compare post-treatment MRI data in erenumab responders to non-responders.

Similar comparisons will be made for pre- and post-treatment pain thresholds (i.e. results of quantitative sensory testing) and cognitive testing.

So as to help with the interpretation of differences between responders and non-responders, MRI data from erenumab-treated patients will be compared to healthy non-migraine control data that we have already collected during the conduction of previous studies, when available (although we have plenty of data for the majority of analyses, we have limited ASL data and no n-back data from healthy controls). Differences in brain structure and function of migraine patients prior to erenumab treatment compared to healthy controls will be identified. Results of this analysis will determine alterations of brain structure and functions in migraine patients compared to healthy controls. Areas where migraine patients show altered structure and function will be used as regions of interest (ROIs) to assess the longitudinal, within-group changes of erenumab responders and non-responders.

Although multiple analyses are planned using functional, structural, and perfusion data, the primary analysis for specific aim #1 will be the comparison of pre-treatment pain-induced regional activation strength vs. post-treatment pain-induced regional activation strength in erenumab responders and separately in erenumab non-responders.

Post-treatment changes in other measures of brain function as well as measures of brain perfusion, brain structure, cutaneous pain thresholds and cognitive function in those responding to erenumab and in those not responding will be explored.

Two-tailed T-Tests or Mann-Whitney U tests will be used to perform group comparisons on demographic and cognitive measures and on pain threshold data. Neuroimaging data will be analyzed using general linear model designs. Within-group changes on cognitive measures, sensory testing and neuroimaging data will be assessed by applying a general linear mixed model design.

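### The responder v non-responder imaging comparison uses post-treatment scans only, so a baseline difference in migraine frequency can pass for normalization; compare pre-to-post change instead

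*Combined protocol and SAP*

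**What the plan says.** Run-in counts may lie anywhere in the entry range ("documented 6-25 migraine days per 28 days", Participants). Response is a relative cut on that single 28-day count: "50% or greater reduction in migraine day frequency between weeks 5-8 post first erenumab treatment compared to frequency during the run-in phase" (Daily Headache Diary).

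The Analysis Plans section, Specific Aim 1, contains two different comparisons:

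- The primary one is "the comparison of pre-treatment pain-induced regional activation strength vs. post-treatment pain-induced regional activation strength in erenumab responders and separately in erenumab non-responders".
- A further one is described as follows: "Between subject group analyses will compare post-treatment MRI data in erenumab responders to non-responders". Similar comparisons are planned for pain thresholds and cognitive tests, with t-tests or Mann-Whitney tests for group comparisons.

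On the imaging model the section says "Neuroimaging data will be analyzed using general linear model designs" and lists no covariates. A general linear mixed model is planned, but for within-group change.

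Published Work and Preliminary Data says of pain-induced activation: "For several of these regions, the extent of greater activation correlated with the frequency of headaches". No coefficient is given.

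**The concern.** The groups are formed from migraine-day counts, and the outcome is one that the protocol itself links to headache frequency. If responders usually have fewer migraine days than non-responders, a comparison of post-treatment images alone carries that difference into the result. Responders would then show lower activation even if treatment changed no one's activation. That is the direction of the study's hypothesis, so the artefact would look like support for it.

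**Working it through.** **The plan's own figure.** Sample Size gives a difference of 0.1% BOLD, SD 0.1, type I error 0.05, 21 per group and 88% power. The standardised effect is 0.1 / 0.1 = 1 SD. A two-sided two-sample t-test with 21 per group and an effect of 1 SD has 88.5% power, so the figure reproduces. That 1 SD is the yardstick below.

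**Is the label easier to earn from a low count?** The drop needed is 3 days from 6, 5 from 10, 10 from 20 and 13 from 25. Take the run-in count b as the true rate, let everyone have the same proportional reduction q, and let the weeks 5-8 count be X ~ Binomial(28, (1 − q)b/28). The chance of response is P(X ≤ b/2). Even counts are used so that rounding of the cut does not distort the slope.

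| q | b = 6 | b = 14 | b = 24 |
|---|---|---|---|
| 0% | 12% | 0.6% | about 0% |
| 40% | 51% | 37% | 24% |
| 50% | 65% | 60% | 58% |
| 60% | 79% | 82% | 88% |

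The slope is steep at small reductions, nearly flat at 50%, and reversed at 60%. The protocol expects about 50% responders, which points towards the flat part.

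**Does the bias depend on that slope?** Only in part. A single 28-day count measures usual frequency with error. A patient whose run-in month happened to be bad meets the cut more easily, so at any given run-in count responders tend to have a lower usual rate. Let D be the difference in usual frequency between the groups, in SD, and r the correlation of activation with usual frequency. If treatment leaves activation unchanged:

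spurious post-treatment gap (SD) = r × D.

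D was obtained by simulating run-in and weeks 5-8 counts. The assumptions were a mean of 13 or 15 migraine days, between-patient SD 5 or 6, day-count overdispersion 0 to 0.1, and pre/post correlation of activation 0.6.

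| Pattern of response | Response rate at 6-8 days | at 20-25 days | D | Gap at r = 0.4 |
|---|---|---|---|---|
| Roughly equal drop in days (mean 5 or 6.5) | 50-69% | 16-47% | 0.70-0.91 | 0.28-0.36 SD |
| Proportional drop (mean 40% or 50%) | 41-52% | 43-64% | 0.13-0.26 | 0.05-0.10 SD |

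In the second row responders start with 0.1 to 1.0 *more* run-in days, yet their usual frequency is still lower. A separate set of simulated response patterns at r = 0.4 gave 0.06 to 0.44 SD. With SD 0.1 that is 0.006% to 0.044% BOLD against the 0.1% design effect. The gap scales with r: 0.03 to 0.22 SD at r = 0.2, and 0.08 to 0.55 SD at r = 0.5.

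**False-positive rate.** For 42 completers and a nominal 5% test, an equal drop in days gives 6.5-9.9% at r = 0.2, 9.7-12.6% at r = 0.3 and 20.4-28.1% at r = 0.5. A proportional drop gives 4.7-7.7%.

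**Remedies under the same null.**

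- *Compare change.* A stable r × D is in both scans and cancels; the simulated gap was within 0.005 SD of zero.
- *Adjust for the pre-treatment value.* With pre/post correlation 0.6, about 1 − 0.6 = 0.4 of the gap remains, so 0.06-0.44 SD becomes about 0.02-0.18 SD.
- *Adjust for run-in days and the pre-treatment value.* False-positive rate 4.2-8.8%.
- *Adjust for run-in days only.* In one scenario with a uniform 50% reduction the gap grew from −0.06 to −0.15 SD. Holding a noisy count fixed sharpens the contrast in usual frequency. Where response weakens with frequency this adjustment can help, but the documents do not say which case applies.

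**The case against.** A reader might infer that a 50% cut is simply easier to reach from a low run-in count, so that responders are the milder patients. The documents do not support that as a general statement. They give no response rate by run-in count, and the first table shows the advantage fading near a 50% reduction and reversing beyond it.

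A reader might also infer that the main test of normalization is compromised. It is not. The primary analysis is pre v post within each group, where a stable baseline difference cancels.

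Other points on that side:

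- The link between activation and frequency is reported for several regions only, for headaches rather than migraine days, and without a coefficient. This stands: every size above rests on an assumed r.
- The gap is small beside 1 SD. This also stands for proportional response; with a uniform 60% reduction, one simulation put it at +0.02 SD, in effect zero.
- A general linear model without listed covariates is not a promise of an unadjusted test, and the protocol mentions correlating imaging with change in migraine days. True, but the diary section offers those correlations only as an option, and nothing commits the responder comparison to using the baseline scan.
- The cited link concerns activation, not pain thresholds or cognition. For those outcomes the case for using the baseline value is consistency, not a demonstrated bias.

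**Conclusion.** The concern holds for the secondary responder v non-responder comparison of post-treatment MRI. As written, it can show lower activation in responders with no treatment effect on activation. At an assumed correlation of 0.4 the spurious gap is about 0.06 to 0.44 SD: the low end if response is roughly proportional, the high end if it favours low-frequency patients. This assumes that activation follows a patient's usual frequency and that the baseline difference is stable over the eight weeks. The primary analysis stands. The point is worth settling before analysis because the artefact runs in the hypothesised direction and the data needed to remove it are already collected.

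**What to change.** In Analysis Plans, Specific Aim 1, state that responder v non-responder comparisons of imaging, pain-threshold and cognitive outcomes will compare pre-to-post change. This can be the group-by-time term in the mixed model already planned for within-group change. The alternative is to adjust the post-treatment value for the pre-treatment value of the same outcome, accepting some residual bias. Do not use run-in migraine days as the sole covariate. Tabulate run-in days and episodic/chronic status by response group beside the results, whichever response definition is finally used.

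Cost: no new data. The SD of a change score is √(2(1 − ρ)) times that of a single value, where ρ is the pre/post correlation. That is 0.89 at ρ = 0.6, 1.00 at 0.5 and 1.26 at 0.2, so precision is lost only if ρ is below 0.5. Covariate adjustment costs one degree of freedom from about 42 patients.
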